**CONFIDENTIAL**

205416 [MENB REC 2ND GEN-038 (V72\_72)]

Statistical Analysis Plan Amendment 9

**CONFIDENTIAL**

205416 [MENB REC 2ND GEN-038 (V72\_72)]

Statistical Analysis Plan Amendment 9

**LIST OF ABBREVIATIONS**

AE	Adverse event
AESI	Adverse Events of Special Interest
ANOVA	Analysis of Variance
CI	Confidence Interval
CRF	Case Report Form
Eli Type	Internal database code for type of elimination code
ELISA	Enzyme-linked immunosorbent assay
EOS	End of Study
ES	Exposed Set
FAS	Full Analysis Set
GMC	Geometric mean antibody concentration
GMT	Geometric mean antibody titre
GSK	GlaxoSmithKline
LL	Lower Limit of the confidence interval
MedDRA	Medical Dictionary for Regulatory Activities
PCD	Primary completion Date
PPS	Per-Protocol Set
RR	Relative Risk
SAE	Serious adverse event
SAP	Statistical Analysis Plan
SD	Standard Deviation
SDTM	Study Data Tabulation Model
TFL	Tables Figures and Listings
TOC	Table of Contents

## 1. DOCUMENT HISTORY

Date	Description	Protocol Version
25 Jul 2019	First version	Amendment 1: 23 MAY 2019
15 Jun 2020	Amendment 1	Amendment 2: 18 MAR 2020
25 Mar 2022	Amendment 2	Amendment 4: 12 MAY 2021
25 Apr 2022	Amendment 3	Amendment 4: 12 MAY 2021
08 Sep 2022	Amendment 4	Amendment 4: 12 MAY 2021
12 Jan 2023	Amendment 5	Amendment 4: 12 MAY 2021
27 Feb 2023	Amendment 6	Amendment 4: 12 MAY 2021
14 Mar 2023	Amendment 7	Amendment 4: 12 MAY 2021
30 Aug 2023	Amendment 8	Amendment 4: 12 MAY 2021
06 Sep 2023	Amendment 9	Amendment 4: 12 MAY 2021

## 2. OBJECTIVES/ENDPOINTS

**Table 1** Study objectives and endpoints

Objectives	Endpoints	
		Primary
Vaccine effectiveness (Test-based): rMenB+OMV NZ To demonstrate the effectiveness of the rMenB+OMV NZ vaccine against a randomly selected panel of endemic US N. meningitidis serogroup B invasive disease strains as measured by bactericidal activity using enc-hSBA at 1 month after the 3-dose (0,2,6-months) and 2-dose (0,6-months; 0,2-months) vaccination series when compared to 1 month after the MenACWY vaccination.	
The percentages of samples without bactericidal serum activity using enc-hSBA against each of the endemic US N. meningitidis serogroup B strains, at 1 month after the:
 
 
3-dose vaccination series in MenB_0_2_6 group (Day 211, Month 7)
 
2-dose vaccination series in MenB_0_6 group (Day 211, Month 7), and
 
2-dose vaccination series in MenB_0_2_6 group (Day 91, Month 3)
 
1 month after the MenACWY vaccination in ACWY group (Day 31, Month 1).
 
	
Effectiveness (Responder-based): rMenB+OMV NZ To demonstrate the effectiveness of the rMenB+OMV NZ vaccine by assessing the percentages of subjects whose sera kill $\geq 70\%$ of strains tested using enc-hSBA at 1 month after the 3-dose (0,2,6-months) and 2-dose (0,6-months; 0,2-months) vaccination series of the rMenB+OMV NZ.	
The percentages of subjects whose sera kill <math>\geq 70\%</math> of the strains tested using enc-hSBA, at 1 month after the:
 
 
3-dose vaccination series (Day 211, Month 7 in MenB_0_2_6 group)
 
2-dose vaccination series (Day 211, Month 7 in MenB_0_6 group),
 
2-dose vaccination series (Day 91, Month 3 in MenB_0_2_6 group)
 
	

**CONFIDENTIAL**

205416 [MENB REC 2ND GEN-038 (V72\_72)]

Statistical Analysis Plan Amendment 9

Objectives	Endpoints

 
MenB_0_2_6 group (for 0,2-months schedule)
 
	

The 3 vaccine schedules will be tested for both, test-based and responder-based, in a hierarchical way (starting from 0-2-6, to 0-6 and 0-2). Refer to Protocol Section 10.1 for details on continuing the evaluation.
	

Lot-to-lot consistency: MenABCWY vaccine
 
To demonstrate lot-to-lot consistency of the immune responses of 3 lots of the MenACWY component of the MenABCWY vaccine, as measured by hSBA GMTs directed against serogroups A, C, W and Y at 1 month after last vaccination (0,6-months).
 
Criterion:
 
The two-sided 97.5% CIs^ for the ratio of hSBA GMTs of antibodies against serogroups A, C, W and Y are within the [0.5;2.0] equivalence interval for each pair of lots.
	
GMTs directed against serogroups A, C, W and Y for each lot (ABCWY-1 group, ABCWY-2 group, ABCWY-3 group) at 1 month after the last vaccination (Day 211, Month 7)

Immunological non-inferiority: MenABCWY vaccine vs. MenACWY vaccine
 
To demonstrate the immunological non-inferiority of the MenABCWY vaccine compared to the MenACWY vaccine as measured by the percentages of subjects achieving a 4-fold rise in hSBA titres against N. meningitidis serogroups A, C, W and Y at 1 month after the last MenABCWY vaccination (0,6-months) and 1 month after the MenACWY vaccination.
 
Criterion:
 
LL of the 2-sided 97.5% CI^ for the group difference in percentages of subjects achieving a 4-fold rise* in hSBA titres is above -10%.
	
The percentages of subjects with 4-fold rise* in hSBA titres against N. meningitidis serogroups A, C, W and Y at 1 month after the:
 
 
last vaccination for the ABCWY group (pooled lots) (Day 211, Month 7), and
 
1 month after the MenACWY vaccination for the ACWY group (Day 31, Month 1) relative to baseline (Day 1, Month 0).
 


Vaccine effectiveness (Test-based): MenABCWY vaccine
 
To demonstrate the effectiveness of the MenABCWY vaccine against a randomly selected panel of endemic US N. meningitidis serogroup B invasive disease strains as measured by enc-hSBA at 1 month after the last MenABCWY vaccination (0,6-months) when compared to 1 month after the MenACWY vaccination.
 
Criterion:
 
LL of the two-sided 97.5% CI^ for vaccine effectiveness is above 65% against a randomly selected strain panel between the ABCWY group (pooled lots) and the ACWY group.
	
The percentages of samples without bactericidal serum activity using enc-hSBA against each of the endemic US N. meningitidis serogroup B strains, at 1 month after the:
 
 
last vaccination for the ABCWY group (pooled) (Day 211, Month 7), and
 
1 month after the MenACWY vaccination in the ACWY group (Day 31, Month 1).
 

Effectiveness non-inferiority: MenABCWY vaccine vs. rMenB+OMV NZ vaccine
 
To demonstrate the non-inferiority of the effectiveness of the MenABCWY vaccine (0,6-months schedule) compared to the rMenB+OMV NZ vaccine (0,2,6-months or 0,6-months or 0,2-months)† in terms of percentage of samples with bactericidal serum activity using enc-hSBA against a randomly selected panel of endemic US N. meningitidis serogroup B invasive disease strains.
	
The percentages of samples with bactericidal serum activity using enc-hSBA against each of the endemic US N. meningitidis serogroup B strains at 1 month after the:
 
 
last MenABCWY vaccination (Day 211, Month 7) for the ABCWY group (pooled lots), and
 
3-dose vaccination series of rMenB+OMV vaccine (Day 211, Month 7 in MenB_0_2_6 group) or 2-dose vaccination series (Day 211, Month 7 in MenB_0_6 group) or 2-dose vaccination series (Day 91, Month 3 in MenB_0_2_6 group)†
 

**CONFIDENTIAL**

205416 [MENB REC 2ND GEN-038 (V72\_72)]

Statistical Analysis Plan Amendment 9

Objectives	Endpoints

Criterion: LL of the two-sided 97.5% CI▲ for the difference in percentages of samples with bactericidal serum activity using enc-hSBA against a randomly selected panel of endemic US N. meningitidis serogroup B invasive disease strains is above -5% at 1 month after:
 
 
• the last vaccination in ABCWY group (pooled lots) (for 0,6 months schedule), and
 
• The last vaccination in MenB_0_2_6 group (for 0,2,6-months schedule) or the last vaccination in MenB_0_6 group (for 0,6-months schedule) or the second vaccination in MenB_0_2_6 group (for 0,2-months schedule)
 
	

Effectiveness (Responder-based): MenABCWY vaccine To demonstrate the effectiveness of MenABCWY vaccine by assessing the percentages of subjects whose sera kill <math>\geq 70\%</math> of strains tested using enc-hSBA at 1 month after the last vaccination of MenABCWY (0,6-months).
 
Criterion: LL of the two-sided 97.5% CI▲ for the percentages of subjects whose sera kill <math>\geq 70\%</math> of strains tested for MenABCWY is above 65%.
	
The percentages of subjects whose sera kill <math>\geq 70\%</math> of the strains tested using enc-hSBA, at 1 month after the last vaccination for the ABCWY group (pooled lots) (Day 211, Month 7).

Safety To evaluate the safety and reactogenicity of the MenB, MenABCWY, and the MenACWY vaccines
	
 
• The frequencies and percentages of subjects with solicited local (i.e., injection site pain, erythema, swelling, induration) and systemic (i.e., fever [body temperature <math>\geq 38.0^{\circ}\text{C}</math>], nausea, fatigue, myalgia, arthralgia, headache) adverse events (AEs) during the 7 days (including the day of vaccination) following each vaccination at Day 1, Day 61 and Day 181.
 
• The frequencies and percentages of subjects with any unsolicited AEs (including all SAEs, AEs leading to withdrawal, AESIs and medically attended AEs) during the 30 days (including the day of vaccination) following each vaccination at Day 1, Day 61 and Day 181.
 
• The percentages of subjects with SAEs, AEs leading to withdrawal, AESIs and medically attended AEs throughout the study period [Month 0 to Month 18].
 


Secondary To demonstrate the immunological non-inferiority of the MenABCWY vaccine compared to the rMenB+OMV NZ vaccine as measured by the percentages of subjects achieving a 4-fold rise in hSBA titres against N. meningitidis serogroup B indicator strains at 1 month after the last MenABCWY vaccination (0,6-months schedule) and 1 month after the rMenB+OMV NZ vaccination (0,2,6-months or 0,6-months or 0,2-months)†
	
The percentages of subjects with 4-fold rise** in hSBA titres against N. meningitidis serogroup B indicator strains at 1 month after the:
 
 
• last MenABCWY vaccination for the ABCWY group (pooled lots) (Day 211, Month 7), and
 
• 3-dose vaccination series of rMenB+OMV vaccine (Day 211, Month 7 in MenB_0_2_6 group) or 2-dose vaccination series (Day 211, Month 7 in
 

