### **3.3. Number of subjects**

A total of 3651 subjects will be randomised in a ratio of 5:5:3:3:3:1; 912 each in MenB\_0\_2\_6 and MenB\_0\_6 groups, 548 in each ABCWY groups and 183 in ACWY group. Assuming a 25% drop out rate, this should provide approximately 684 evaluable subjects in each of the MenB groups, 411 evaluable subjects in each of the ABCWY groups and 137 evaluable subjects in the ACWY group.

Refer to Protocol Section 10.1 for a detailed description of the criteria used in the determination of sample size.

Withdrawals will not be replaced.

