#### **4.1.6. Unsolicited Safety Set**

All subjects who received at least 1 dose of the study treatment (Exposed Set) that report unsolicited AEs/report not having unsolicited AEs.

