#### **4.1.7. Overall Safety Set**

All subjects that belong to the Unsolicited safety or/and to the Solicited safety set.

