	
Endpoints description: The frequencies and percentages of subjects with any unsolicited AEs (including all SAEs), AEs leading to withdrawal and medically attended AEs during the 7 and the 30 days (including the day of vaccination) following each vaccination at Day 1, Day 61 and Day 181.
 
The frequencies and percentages of subjects with SAEs, AEs leading to withdrawal, AESIs and medically attended AEs throughout the study period.
 
This analysis applies to all adverse events occurring during the study, judged either as possibly related, or not related to vaccination by the investigator, recorded in AE CRF, with a start date on or after the date of first vaccination. AE starting prior to the first vaccination will only be listed.
 
The original verbatim terms used by investigators to identify adverse events in the CRFs will be mapped to preferred terms using the MedDRA dictionary. The adverse events will then be grouped by MedDRA preferred terms into frequency tables according to system organ class.
 
All reported adverse events, as well as adverse events judged by the investigator as possibly related to study vaccine, will be summarised according to system organ class and preferred term within system organ class. These summaries will be presented by vaccine group and by interval of study observation. When an adverse event occurs more than once for a subject, the maximal severity and strongest relationship to the vaccine group will be counted.
 
Separate summaries will be produced for the following categories:
 
 
• Serious adverse events.
 
• Adverse events that are possibly related to vaccine.
 
• Adverse events of special interest.
 
• Adverse event leading to withdrawal.
 
• Adverse events leading to a medically attended visit.
 
 
Data listings of all adverse events will be provided by subject. In addition, adverse events in the categories above will be provided as listed data.
 
Local and systemic AEs will be analyzed by point estimates with associated 95% CIs [Clopper, 1934].

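### The Month 0 to 18 safety percentages make no allowance for subjects lost before Day 541, so they understate 18-month occurrence by an amount that depends on how many are lost and when

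*SAP*

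**What the plan says.** The third safety endpoint in SAP Section 2, Table 1 is "The percentages of subjects with SAEs, AEs leading to withdrawal, AESIs and medically attended AEs throughout the study period [Month 0 to Month 18". Section 5.5.1 carries it forward in the same form, beginning "The frequencies and percentages of subjects with SAEs". The estimator there is a count and a percentage, and no person-time rate or time-to-event estimate is mentioned.

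Section 5.5.1 lists the Solicited, Unsolicited and Overall Safety Sets but does not say which one serves the Month 0 to 18 row. For this point the choice makes no difference:

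- The Unsolicited Safety Set (Section 4.1.6) is "All subjects who received at least 1 dose of the study treatment (Exposed Set) that report unsolicited AEs/report not having unsolicited AEs".
- The Overall Safety Set (Section 4.1.7) is "All subjects that belong to the Unsolicited safety or/and to the Solicited safety set".

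Neither requires a minimum length of follow-up. Under Section 4.2.3 the only exclusions that depend on safety data are codes 1150 and 1160, for subjects with no such data at all after vaccination.

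Section 3.3 gives the planning loss: "Assuming a 25% drop out rate, this should provide approximately 684 evaluable subjects in each of the MenB groups". It adds "Withdrawals will not be replaced". Section 3.4 counts a subject as complete if available at the Day 541 contact. The missing-data rules in Section 10.1.2 cover partial dates, laboratory results, diary entries and missing AE attributes. They do not cover follow-up cut short.

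**The concern.** An event can be counted only while the subject is still in contact. A subject who answers one early safety enquiry and is then lost stays in the denominator for all 18 months but can add to the numerator only for the weeks observed. In effect the rest of the period is scored as free of SAEs, AESIs and medically attended AEs. The percentage is labelled as covering Month 0 to Month 18, so a reader will take it as the 18-month risk.

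What is at stake is the absolute level of a primary safety figure. The last study visit is Day 211 and the closing telephone contact is Day 541, 330 days later, so there is ample time for loss. Dosing is also staggered: an ABCWY subject lost before Day 181 never receives the second dose of the investigational vaccine but still counts in that group's 18-month figure. If loss differed between groups, the group with more loss would tend to look safer.

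**Working it through.** **Reproducing the plan's own figure.** Section 3.3 randomises 912 subjects to each MenB group and "548 in each ABCWY groups and 183 in ACWY group". Taking off 25%:

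- 912 × 0.75 = 684
- 548 × 0.75 = 411
- 183 × 0.75 = 137.25, given as 137

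These match the SAP.

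**Inputs.** Follow-up is 18 months (Day 541) and d is the proportion lost to safety follow-up. The SAP gives 25% as drop-out in relation to evaluable subjects. It gives neither the timing of drop-out nor the timing of events, so both are assumptions here and are varied.

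**Formula.** Let p be the true 18-month occurrence and λ = −ln(1 − p)/18 per month (constant hazard). Then

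observed = (1 − d) × p + d × mean of [1 − exp(−λt)] over drop-out times t.

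For rare events the relative understatement reduces to d × (1 − mean follow-up of those lost / 18).

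**All 25% lost, constant hazard, rare events:**

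- Loss uniform over Months 0 to 18: 0.25 × (1 − 9/18) = 12.5%
- Loss uniform over Months 0 to 7: 0.25 × (1 − 3.5/18) = 20.1%
- Loss uniform over Months 7 to 18: 0.25 × (1 − 12.5/18) = 7.6%
- Ceiling, all lost at the start: 25%. This is a bound only, because a subject with no post-vaccination safety data is removed from the set.

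**Illustrative absolute figures (p assumed, d = 25%):**

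| True 18-month occurrence | Reported, loss over Months 0–18 | Reported, loss over Months 0–7 |
|---|---|---|
| 20% | 17.6% | 16.1% |
| 2% | 1.75% | 1.60% |

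For p = 20% and loss over Months 0 to 18: 18λ = 0.2231. The mean for those lost is 1 − 0.20/0.2231 = 0.104, and 0.75 × 0.20 + 0.25 × 0.104 = 0.176.

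For more common events the relative effect is slightly smaller. At p = 30% to 50% it is 11.8% to 11.1% (Months 0–18) and 19.5% to 18.8% (Months 0–7).

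**Smaller safety loss (constant hazard):**

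| d | Loss over Months 0–18 | Loss over Months 0–7 |
|---|---|---|
| 10% | 5.0% | 8.0% |
| 5% | 2.5% | 4.0% |

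**Events clustered after vaccination.** Suppose half of all events fall in the 30 days after the Day 1, Day 61 and Day 181 vaccinations and the rest are spread evenly, with d = 25%. The understatement becomes d × (1 − mean share of events already seen at drop-out): 8.4% (loss over Months 0–18), 15.7% (Months 0–7) and 3.8% (Months 7–18).

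**The case against.** The strongest reply is that the SAP does what it sets out to do. The endpoint is defined as a percentage of subjects and is analysed as one. The objective is descriptive, with no hypothesis, margin or alpha attached, so no decision rule moves. That stands: this is not a contradiction in the SAP.

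A reader might infer that the percentages will be 12 to 20% too low. The SAP does not support that as a statement of fact. Section 3.3 ties the 25% to evaluable subjects. Table 4 removes subjects from the Per Protocol Set for missed blood-sampling windows, missing serology or sample-handling faults (codes 2090, 2100, 2120, 2130), and such subjects can still give safety data to Day 541. The 25% is better read as an upper planning value for safety loss.

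A reader might also infer that the comparison between groups is biased. Nothing in the SAP points to unequal loss. The trial is randomised and observer-blind, reasons for early withdrawal are reported by group (Section 5.1.1), and a withdrawal recorded as due to an AE is itself counted in this endpoint. With similar loss in each group the comparison is little affected. The 30-day windows and the summaries by interval also reduce reliance on the 18-month figure.

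Finally, Kaplan-Meier estimation assumes non-informative loss, so it would not cure loss driven by tolerability. That is right, and is a reason to keep the crude figure beside it. None of these points removes the downward direction for absolute 18-month occurrence.

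**Conclusion.** The point holds in direction, and its size is conditional. With no minimum follow-up in either candidate set and no adjustment in Section 5.5.1 or 10.1.2, the Month 0 to 18 percentages understate 18-month occurrence whenever subjects are lost while still at risk of a first event. About 12% to 20% is the relative understatement only if all 25% are lost to safety follow-up, the event rate is constant, and loss is spread over Months 0 to 18 or complete by Month 7. Loss of 5 to 10% gives about 2.5 to 8%, and clustering of events after vaccination lowers every figure. The actual size cannot be determined from the SAP. The effect is on reported absolute risk in a primary but descriptive safety endpoint. No success criterion depends on it.

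**What to change.** In Section 5.5.1, name the analysis set for the Month 0 to 18 row and keep the crude n/N. Beside it, add by group one of the following, with 95% confidence intervals:

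- Kaplan-Meier cumulative incidence at Month 18
- subjects with an event per 100 person-years

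Time runs from first vaccination to first event or last safety contact. Also show total person-time and the percentage followed to Day 541 by group, and state that the added estimate assumes non-informative loss.

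The cost is a short change to the SAP wording and one extra table column, with slightly less favourable absolute rates. It needs a date of last safety contact for each subject. The scheduled telephone follow-up makes that likely to exist, but the SAP does not say so and it should be confirmed.

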## CONFIDENTIAL

205416 [MENB REC 2ND GEN-038 (V72\_72)]

Statistical Analysis Plan Amendment 9

Objectives	Endpoints

Criterion:
 
Non-inferiority will be demonstrated if the LL of the 2-sided 95% CI for the group difference in percentage of subjects achieving a 4-fold rise** in hSBA titres against N. meningitidis serogroup B indicator strains is above -10%.
	
MenB_0_6 group) or 2-dose vaccination series (Day 91, Month 3 in MenB_0_2_6 group)† relative to baseline (Day 1, Month 0).

To assess the effectiveness of the rMenB+OMV NZ and MenABCWY vaccines against each of the randomly selected endemic US N. meningitidis serogroup B invasive disease strains as measured by bactericidal activity using enc-hSBA at 1 month after the 3-dose (0,2,6-months in MenB_0_2_6 group) and 2-dose (0,6-months in MenB_0_6 group, 0,2-months in MenB_0_2_6 group and 0,6-months in the ABCWY (pooled) group) vaccination series when compared to 1 month after the MenACWY vaccination.
	
The percentages of samples without bactericidal serum activity using enc-hSBA against each of the endemic US N. meningitidis serogroup B strains at 1 month after the:
 
 
3-dose vaccination series (Day 211, Month 7 in MenB_0_2_6 group)
 
2-dose vaccination series (Day 211, Month 7 in MenB_0_6 group)
 
2-dose vaccination series (Day 91, Month 3 in MenB_0_2_6 group)
 
last vaccination for the ABCWY group (pooled lots) (Day 211, Month 7), and
 
MenACWY vaccination (Day 31, Month 1 in ACWY group).
 

To describe the distribution of subjects by percentages of serogroup B invasive disease strains killed using enc-hSBA at 1 month after the 3-dose (0,2,6-months in MenB_0_2_6 group) and 2-dose (0,6-months in MenB_0_6 group, 0,2-months in MenB_0_2_6 group and 0,6-months in the ABCWY (pooled) group) vaccination series of rMenB+OMV NZ and MenABCWY vaccines.
	
The percentages of serogroup B invasive disease strains killed using enc-hSBA in each subject at 1 month after the:
 
 
3-dose vaccination series (Day 211, Month 7 in MenB_0_2_6 group)
 
2-dose vaccination series (Day 211, Month 7 in MenB_0_6 group)
 
2-dose vaccination series (Day 91, Month 3 in MenB_0_2_6 group), and
 
last vaccination for the ABCWY group (pooled lots) (Day 211, Month 7)
 


To assess the immune response to the rMenB+OMV NZ (0,2,6-months, 0,6-months and 0,2-months) and MenABCWY (0,6-months) vaccines against N. meningitidis serogroup B indicator strains at pre-vaccination (Day 1, Month 0) and at 1 month after the last MenABCWY vaccination and at 1 month after the second and third vaccination of rMenB+OMV NZ.
	
The immune response to the rMenB+OMV NZ and ABCWY vaccines will be evaluated by measuring bactericidal activity against N. meningitidis serogroup B indicator strains as following:
 
 
The percentages of subjects with hSBA titres <math>\geq</math> lower limit of quantitation (LLOQ) for each (individual response) and all (composite response) serogroup B indicator strains at baseline (Day 1, Month 0) and at 1 month after the: 
 
3-dose vaccination series (Day 211, Month 7 in MenB_0_2_6 group)
 
2-dose vaccination series (Day 211, Month 7 in MenB_0_6 group)
 
2-dose vaccination series (Day 91, Month 3 in MenB_0_2_6 group), and
 
last vaccination for the ABCWY group (pooled lots) (Day 211, Month 7)
 
 
 
The percentages of subjects with 4-fold rise** in hSBA titres at 1 month after the: 
 
3-dose vaccination series (Day 211, Month 7 in MenB_0_2_6 group)
 
 
 

